The medical professionals were not blinded to PHE data at the time of diagnosis. These data were not routinely used to inform diagnoses, but instead used to identify functional rehabilitation targets and for benchmarking. Following injury, players completed a rehabilitation programme as directed by club medical staff to enable them to return to training and match participation.

Participants and eligibility criteria

Eligible participants were identified from a review of the PHE database entries during the dates stated above. During any season, participants were eligible for inclusion into the analysis if they: 1) were aged between 16-40 years; 2) had an outfield position (i.e. not a goalkeeper); 3) participated in PHE testing for the relevant season. Participants were excluded from the analysis for any season if they were a triallist player or not contracted to the club at the time of PHE.

Ethics and Data Use

Because all data were captured from the mandatory PHE completed through the participants' employment, informed consent was not required. The anonymity and rights of all players were protected. The football club granted permission to use these data and the use of the data for this study was approved by the Research Ethics service at the University of Manchester.

This study has been registered on ClinicalTrials.gov, with registered number

as

Data extraction

All PHE records from eligible participants were extracted and placed into a separate database. Using the club's electronic medical records system, a further database was generated of all recorded injuries for each season and a manual review of each eligible participant's medical record was undertaken to ensure accuracy. Each injury was categorised according to: 1) contact or non-contact mechanism of injury; 2) injured side; 3) affected body area; 4) injury type i.e. IMI/ligament/tendon/cartilage/contusion or

laceration/bone/concussion/other musculoskeletal injury; 5) muscle group and diagnostic classification if recorded as an IMI. This process allowed an in-house audit of injury incidence and absolute risk evaluation for each injury type for the squad overall and for those who underwent PHE. All IMIs were then extracted and merged with the PHE database of included participants, for each season in which they remained eligible.

Outcome Measures

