The primary outcome measure for both studies will be the occurrence of an initial (index) lower extremity IMI sustained by a participant during a season. Only time-loss injuries will be included; that is, any index lower extremity IMI that occurred during match play or training that resulted in the player being unable to take full part in future match play or training (30). An IMI was confirmed during the injury assessment procedure outlined above, and graded by the club doctor or physiotherapist according to the Munich Consensus Statement for the Classification of Muscle Injuries in Sport (4). This diagnostic classification system is the primary method of muscle injury classification used by the club and has been validated previously (31).

If an index lower extremity IMI occurred, the participant's outcome for the season will be determined and that participant will no longer be considered at risk beyond the time of IMI occurrence. In these circumstances, participants will be included for further analysis at the start of the consecutive season, providing they remain eligible. If participants sustained any upper limb IMI or non-IMI injury type, these will be ignored and the participant will still be considered at risk of a lower extremity index IMI.

Each participant-season will be treated as independent. Eligible participants who were loaned out or transferred to another club throughout that season, but had not sustained an index IMI prior to the loan or transfer will still be considered in the risk set. Participants who sustained an index IMI while on loan will be included for analysis, as outlined above. Any participants who were permanently transferred during a season (anticipated to be very few) will be recorded as not having an IMI event during the relevant season and they will exit the cohort at this point. A sensitivity analysis may be conducted to evaluate the effect of player loans or transfers on the results.

If there are a sufficient number of index IMI outcomes, secondary analyses may be performed, which may include outcomes of hamstring muscle IMIs, functional IMIs (classified as type 1A to 2B), or structural IMIs (classified as type 3 or 4) according to the Munich Consensus Statement criteria.(4)

Sample Size

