As this study will retrospectively utilise the available dataset, a formal sample size calculation has not been conducted, as the total sample size and IMI outcomes are already fixed. To maximise power, we have elected to use all data from the 5-season period. This approach agrees with methodological recommendations that data splitting should be avoided, and all available data should be used for model validation (32).

The number of candidate PFs for inclusion in model development will be restricted to be a minimum of 10 events per variable, which is recommended to reduce overfitting and

optimism during development of a logistic regression model (33). Note that ‘variable’ here means a parameter included (or considered for inclusion) in the model that corresponds to one of the PFs. Although data cleaning for the final season is still in progress, we anticipate that the minimum number of index IMIs will be 100, so will restrict to 10 candidate PFs (variables) for inclusion in the model.

Assuming the model will have a modest R Nagelkerke-squared of 25%, then with an anticipated outcome proportion of 0.381, our 10 events per variable restriction corresponds to targeting an expected shrinkage of 0.85, and thus a relatively small amount of overfitting (15%) (34).

Candidate prognostic factors

A complete list of 60 candidate PFs extracted from the PHE dataset is presented in Table 1.

Table 1: Candidate prognostic factors extracted from PHE data

Type of Prognostic Factor	Candidate Prognostic factor	Measurement method	Data type
Anthropometrics	Age	Date of birth	Continuous
	Height	Standing height measure	Continuous
	Weight	Digital scales	Continuous
	Body fat	Skin callipers	Continuous
	BMI	Composite height (cm) and weight (kg)	Continuous
Medical history	Frequency of previous muscle injuries within 3 years prior to PHE	Medical records	Discrete (treated as continuous)
	Most recent previous muscle injury within 3 years prior to baseline PHE	Medical records	Categorical
	Frequency of previous foot or ankle injuries within 3 years prior to PHE	Medical records	Discrete (continuous)
	Most recent previous foot or ankle injury within 3 years prior to PHE	Medical records	Categorical

	Frequency of previous hip or groin injuries within 3 years prior to PHE	Medical records	Discrete (continuous)
	Most recent previous hip or groin injury within 3 years prior to PHE	Medical records	Categorical

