Because only 10 PFs will be used in model building, we have defined these candidate PFs *a priori*, (Table 2). Three candidate PFs have known importance based on the results of our previous systematic review so were selected for inclusion (22). All other PFs listed in Table 1

were eligible unless there were >15% missing observations or if reliability (where applicable) was classed as fair to poor (ICC < 0.70) (35). In these cases, the relevant candidate PFs were excluded (Table 3). This was to ensure that only the highest quality data will be used in the analysis, with PFs that would generally be available and routinely measured.

Co-linearity amongst factors within a logistic regression model can cause inaccuracies in standard error and confidence interval estimates (36) so a scatterplot matrix was used to informally assess between-factor correlations for eligible PFs. If PFs were highly correlated, one of the PFs were dropped or new composite PFs were generated and replaced the original factors (highlighted in Tables 2-4). Typically, this occurred where measurements examined both right and left limbs separately; composite factor variables were therefore created for both between-limb measurement differences and the mean of the measurements for both limbs.

Of the remaining eligible PFs, 7 further candidate factors were selected for inclusion, through use of clinical reasoning to identify those with a biologically plausible association with IMI development. The final set of 10 PFs is shown in Table 2.

Table 2: Restricted set of candidate prognostic factors for model development and validation.

Selection method	Candidate Prognostic factor	Composite PF	Measurement unit	Measurement method	Data type	Reliability (if applicable)
Systematic review	Age	No	Years & days	Date of birth	Continuous	N/A
	Frequency of previous muscle injuries within 3 years prior to PHE	No	Count	Medical records	Discrete (treated as continuous)	N/A
	Most recent previous muscle injury within 3 years prior to baseline PHE	No	< 6 months, 6-12 months, > 12 months	Medical records	Categorical	N/A
Clinical reasoning/ data quality	CMJ power	No	Normalised peak force (N/Kg ^{-0.67})	CMJ using force plates	Continuous	Test-retest ICC = 0.92-0.98.(37)
	PROM hip joint internal rotation difference*	Yes	Degrees	Digital inclinometer	Continuous	Intra-rater ICC= 0.90.(38)
	PROM hip joint external rotation difference*	Yes	Degrees	Digital inclinometer	Continuous	Intra-rater ICC = 0.90.(38)

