Multivariable logistic regression will be used for the analysis as this is an appropriate method where outcomes are binary (26) and independent variables (PFs) are continuous, categorical or a combination (36). Initially we will fit a full multivariable model containing all 10 candidate PFs to ensure a fully adjusted model prior to potential elimination of unimportant candidate factors (23). Backward elimination will then be used to successively remove non-significant factors with p-values of greater than 0.157. This threshold was set to approximate equivalence with Akaike's Information Criterion (48). Using backward elimination in this way may deliver a more parsimonious model which is therefore easier to implement in clinical practice than a full model. Where possible, we will retain continuous candidate PFs in their continuous form to avoid statistical power loss (49).

We will assume that any missing data are missing at random (MAR) so multiple imputation (MI) will be used, using 50 imputations for missing values. We have chosen to utilise MI because it avoids excluding participants from the analysis, is an effective method of handling missing prognostic factor information and can be used to account for uncertainty in missing data (50).

The apparent performance of the developed model will be summarised in the development datasets (averaged over imputation datasets), via calibration and discrimination. Model calibration determines performance in terms of the agreement between predicted outcome

risks and those actually observed (51). Graphical plots are useful to assess calibration (23), so will be produced and utilised in the analysis. We will calculate calibration-in-the-large (CITL, ideal value of 0), which quantifies the systematic error in model predictions (overall agreement). A related measure is E/O (ideal value of 1), which gives the ratio of the mean of the predicted risks against the mean of the observed risks (O) (51, 52). A calibration slope will also be calculated, where a value of 1 equals perfect calibration (26). Models demonstrate perfect calibration within development data, but in new data the slope may be <1 due to overfitting in the model development dataset (see below for how this will be handled) (52).

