Discrimination performance is a measure of a model's ability to separate participants who have experienced an outcome compared to those who have not, quantified using the C (concordance) statistic (equivalent to the area under the ROC curve) (23). This index measure will be calculated for the development model, where 1 demonstrates perfect discrimination, while 0.5 indicates that discrimination is no better than by chance alone.

To quantify the degree of optimism due to overfitting, our model will be internally validated using bootstrap re-sampling. This will be conducted as previously outlined (26, 53). The prognostic factor variable selection procedure and model construction will be repeated for 200 bootstrap samples. For each sample, the difference in bootstrap apparent performance (of the bootstrap model in the bootstrap data) and test performance (of the bootstrap model in the original dataset) will be averaged across the 200 samples, to obtain a single estimate of optimism for each performance statistic. Then, to calculate optimism-adjusted estimate of

performance for our new model, the estimates of optimism will be subtracted from the original apparent estimates of performance.

The optimism-adjusted calibration slope will provide a uniform shrinkage factor, which will be applied to all prognostic factor effects in the developed model to adjust (shrink) for overfitting. The intercept of the model will then be re-estimated accordingly. This will then form our final model.

Prognostic factor exploration

All candidate factors eligible for the exploratory study will undergo univariable logistic regression analyses to determine unadjusted associations with IMIs. Candidate PFs will be grouped according to PF type (Table 4) and incorporated into multivariable logistic regression models to determine regression coefficients and odds ratios after adjustment for age, BMI, frequency of previous IMIs and most recent IMI within the 3 years prior to PHE, (which were included as candidates in the original model). During multivariable analysis of the anthropometric candidate factors, BMI will not be included in these models due to collinearity with height and weight factors. Exploration of non-linear associations between candidate factors and index IMI outcomes will be evaluated using a fractional polynomial approach (49). This analysis will allow examination of added prognostic value over and above other factors included in the original model.

DISCUSSION

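### Does it matter that the five between-limb differences in the model are not defined as signed or absolute?

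*Combined protocol and SAP*

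**What the plan says.** Under Model development and internal validation, the plan explains that right and left measurements were typically highly correlated, and that "composite factor variables were therefore created for both between-limb measurement differences and the mean of the measurements for both limbs". Table 2 then lists five differences among its 10 factors: hip internal rotation, hip external rotation, hip flexor length, hamstring length/neural mobility and calf length. They are five of the seven factors chosen by clinical reasoning. Table 4 carries three more, all from the leg extension test. The table keys explain the asterisk only as marking a between-limb difference.

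Other parts of the plan that bear on the point:

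- **Outcome Measures.** The outcome is the "occurrence of an initial (index) lower extremity IMI sustained by a participant during a season", on either side.
- **Data extraction.** Each injury was categorised by "2) injured side; 3) affected body area", among other items, but side does not enter the outcome. Table 1 has no limb dominance.
- **Sample Size.** A variable is "a parameter included (or considered for inclusion) in the model that corresponds to one of the PFs", with 10 allowed for 10 factors.
- **Statistical analysis.** In the model, where possible, "we will retain continuous candidate PFs in their continuous form to avoid statistical power loss". Non-linear forms are named only under Prognostic factor exploration: "Exploration of non-linear associations between candidate factors and index IMI outcomes will be evaluated using a fractional polynomial approach".

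**The concern.** A right-minus-left difference and its absolute value carry different information. Suppose right and left are exchangeable, which is an assumption. The risk of an injury in either limb is then the same for a player 5 degrees tighter on the right as for one 5 degrees tighter on the left. Risk is an even function of the signed difference, and a single linear signed term has expected slope zero however strongly asymmetry matters. If the five factors were coded that way, half of the 10-parameter allowance would go to terms unable to show the effect they were chosen for, and their elimination could be misread as evidence that asymmetry is unimportant.

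Two further points seem to add weight. The reliability coefficients printed beside the differences in Table 2 match those printed beside the means in Table 4, so they look like single-limb values; a difference between two correlated readings is usually less repeatable than either reading. And injury data were already linked: "All IMIs were then extracted and merged with the PHE database of included participants". A coding chosen after seeing results would lie outside the internal validation, where "The prognostic factor variable selection procedure and model construction will be repeated for 200 bootstrap samples".

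**Working it through.** **1. The plan's own figure.** Sample Size gives at least 100 events, outcome proportion 0.381, Nagelkerke R-squared 0.25, 10 parameters and expected shrinkage 0.85.

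- n = 100/0.381 = 262.
- Maximum Cox-Snell R-squared = 1 − exp{2[0.381 ln 0.381 + 0.619 ln 0.619]} = 0.735, so the anticipated value is 0.25 × 0.735 = 0.184.
- Solving n = 10/[(S − 1) ln(1 − 0.184/S)] at n = 262 gives S = 0.845, which agrees with the stated 0.85.

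Either coding uses one parameter per factor, so this figure does not depend on the choice. Entering signed and absolute terms together for all five differences would give 15 parameters, 100/15 = 6.7 events per parameter and shrinkage of about 0.79. Hedging with both would therefore cost something.

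**2. How different the codings are.** For a normal difference D with SD 1, the correlation between D and |D| depends on mean asymmetry:

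| Mean asymmetry (SD) | 0 | 0.25 | 0.5 | 1 |
|---|---|---|---|---|
| Correlation | 0.00 | 0.32 | 0.57 | 0.86 |

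**3. Consequence for selection.** Logistic simulation: 262 player-seasons, one predictor, event proportion 0.381, retention at p<0.157, 4,000 data sets. The effect sizes are assumptions.

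| Risk depends on | Mean asymmetry (SD) | Absolute term kept | Signed term kept |
|---|---|---|---|
| Size, OR 1.62 per SD of the difference | 0 | 81% | 17% |
| Same | 0.25 | 83% | 29% |
| Same | 0.5 | 86% | 52% |
| Same | 1 | 95% | 88% |
| Direction, OR 1.34 per SD | 0 | 15% | 81% |

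A re-run agreed to within about 2 percentage points.

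**4. How far the contrast rests on its assumptions.** Step 3 treats the difference as measured without error. With zero mean asymmetry and the same true effect, signed reliability of 0.80 lowers absolute retention to about 64%, and reliability of 0.667 lowers it to about 50%; the signed term stays near 17%. Halving the log odds ratio, without error, gives about 40% against 17%. The gap persists but narrows.

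**5. Reliability.** If the printed coefficient k is a single-limb value, r is the right-left correlation and errors are independent, a signed difference has reliability (k − r)/(1 − r) and a mean has (k + r)/(1 + r). With k = 0.90 and an assumed r = 0.7:

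- difference: 0.20/0.30 = 0.67
- mean: 1.60/1.70 = 0.94

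The two would not normally share one value, which supports reading the column as describing the test. The exclusion rule (ICC below 0.70) is applied to the factors listed in Table 1, which are single-limb measures, and it is met there. The documents do not give r, so no factor is shown to fail.

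**6. What the text implies about coding.** The composites are described in the past tense as already created and as having replaced the original measures, and the 10 factors are declared a priori. So a coding exists, though it is not printed. The factors were chosen for a biologically plausible link with muscle injury, the outcome ignores side, and dominance is not recorded. A right-minus-left difference has little rationale in that design; size of asymmetry does.

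**The case for a change.** The strongest case for acting is that the protocol is the public record, that half the model's candidates cannot be rebuilt from it, and that one formula per factor would settle the matter at almost no cost. Nothing printed says absolute, and under a signed reading the loss in step 3 is real.

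Part of this stands. The definition is absent, the count of five in 10 is correct, and the final equation cannot be applied to a new player until the coding is given. That last need is met when the model is reported, and the plan commits to TRIPOD reporting.

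The rest is weaker:

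- The harm needs signed coding, which the plan nowhere states, together with a single linear term, which is inferred. The ten-for-ten count does not prove one term per factor, because Table 2 also holds a categorical factor with three printed levels.
- The worry about choosing the coding after seeing results has no support in the text, given that the composites already exist.
- The chance that at least one of five independent null terms is kept, 1 − (1 − 0.157)^5 = 57%, holds for any five null candidates and is not a result of the coding.
- The reliability point breaches no rule of the plan and rests on cited studies that were not available for this review.

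**Conclusion.** No change to the plan is needed. The documents leave out a definition that the analysts must already have applied in building the dataset, and the reading that fits an either-limb outcome is size of asymmetry, under which the analysis does what it sets out to do. Asking for the formula would record an existing choice; it would not correct a stated method, and the 10 parameters and expected shrinkage of about 0.85 would be unaffected.

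The possible loss is large only under a combination the documents do not establish: signed coding, one linear term, exchangeable limbs and little average asymmetry. Under that combination, retention falls from 81% to 17% with error-free measurement, or from roughly 50–64% to 17% with plausible error. With 1 SD of average asymmetry the difference is 95% against 88%. The effect sizes, mean asymmetry and right-left correlation are all assumptions.

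The calf difference is listed as composite 'No' in Table 2 although it carries the asterisk, and Table 4 marks the calf mean as composite. That is clerical and has no effect on the analysis.

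### The only calibration plot described is of apparent performance in the development data; no planned curve shows calibration across the risk range after allowing for overfitting

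*Combined protocol and SAP*

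**What the plan says.** All of this is in the combined protocol and SAP, Statistical analysis, Model development and internal validation.

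- The calibration paragraph opens by fixing its scope: "The apparent performance of the developed model will be summarised in the development datasets (averaged over imputation datasets), via calibration and discrimination".
- Plots are mentioned once, in that paragraph: "Graphical plots are useful to assess calibration (23), so will be produced and utilised in the analysis". The sentence names neither a model nor a dataset.
- The same paragraph adds: "Models demonstrate perfect calibration within development data, but in new data the slope may be <1 due to overfitting", and points forward to the handling of overfitting.
- Internal validation then follows: "The prognostic factor variable selection procedure and model construction will be repeated for 200 bootstrap samples". Apparent and test performance are compared "to obtain a single estimate of optimism for each performance statistic". No plot or curve is mentioned here.
- Last comes the correction: "The optimism-adjusted calibration slope will provide a uniform shrinkage factor" for all coefficients. "The intercept of the model will then be re-estimated accordingly". "This will then form our final model". No performance summary of that final model is described.

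The Sample Size section gives the expected shrinkage (0.85), the assumed Nagelkerke R-squared (25%), the outcome proportion (0.381), the minimum number of events (100) and the number of candidate variables (10). The Discussion says there are no immediate plans for external validation.

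**The concern.** The model is meant to give individual absolute risks that guide prevention, so it matters whether a predicted 70% is really about 70%. With no external validation in prospect, internal validation is the only evidence on this for now.

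Of the planned calibration measures, calibration-in-the-large and E/O are overall averages, close to 0 and 1 by construction in development data, and the slope is one number. Only a curve shows where along the risk range the predictions go wrong. The curve is also the natural check on non-linear misfit, because fractional polynomials are specified only for the exploratory factors and not for the ten-factor model.

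As written, the curve is drawn on the data that built the model. For the unshrunken model its overall slope is about 1 however much the model is overfitted. For the shrunken model the same data would give a slope above 1. The plan does not say which model is plotted.

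**Working it through.** **Inputs** (Sample Size section): 100 events, outcome proportion 0.381, P = 10 parameters, Nagelkerke R-squared 0.25, expected shrinkage S = 0.85. Hence N = 100/0.381 = 262.5, or about 262 participant-seasons.

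**1. Reproduce the plan's 0.85.**
- Null log-likelihood per participant-season: 0.381 ln 0.381 + 0.619 ln 0.619 = −0.6646.
- Maximum Cox-Snell R-squared: 1 − exp(2 × −0.6646) = 0.735. Assumed value: 0.25 × 0.735 = 0.184.
- Solve N = P / [(S − 1) ln(1 − R²/S)] for S. At N = 262.5, S = 0.845. Exactly 0.85 needs N = 274 (104 events).

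The plan's figure is reproduced to rounding.

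**2. Unshrunken model on its own data.** A maximum-likelihood logistic fit has an apparent slope of 1. With pooled imputations it is about 1. The slope expected in new data is about 0.85.

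Approximate size on the risk scale: take the distance of the predicted logit from m = logit(0.381) = −0.485, multiply by S, and transform back, so expected risk = expit[m + 0.85 (logit q − m)].

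| Predicted q | logit q | Shrunken logit | Expected risk | Difference |
|---|---|---|---|---|
| 70% | 0.847 | 0.647 | 65.6% | −4.4 points |
| 80% | 1.386 | 1.106 | 75.1% | −4.9 points |
| 10% | −2.197 | −1.940 | 12.6% | +2.6 points |

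**3. Shrunken model on the same data.** If the apparent slope is 1 and every coefficient is multiplied by S, regressing the outcome on the shrunken linear predictor gives a slope of 1/S. That is 1/0.85 = 1.18 (1/0.845 also rounds to 1.18).

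**4. What a corrected curve would show at S = 0.85.** A slope of about 0.85 for the unshrunken model, and about 0.85/0.85 = 1.00 for the final model.

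**5. Simulation check.** Assumptions beyond the plan: 10 independent normal predictors and no missing data. Otherwise n = 262, R-squared 0.25 and elimination at 0.157, with 40 datasets and 50 bootstraps each.

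| Effect pattern | Apparent slope | Mean new-data slope | Mean bootstrap S | Mean development slope after shrinkage (5th–95th percentile) |
|---|---|---|---|---|
| Ten equal effects | 1.000 | 0.75 | 0.80 | 1.25 (1.18–1.36) |
| A few strong effects | 1.000 | 0.87 | 0.83 | 1.21 (1.15–1.30) |

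The apparent slope was 1.000 in every dataset, so it carried no information about overfitting.

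**The case against.** The strongest reply is that the substance is already dealt with. Selection is repeated in every bootstrap sample, optimism is subtracted from each statistic, and the adjusted slope then shrinks the model. That stands. A reader might infer from the table in step 2 that the final model will be wrong by 3 to 5 points. The documents do not support this: those differences belong to the model before shrinkage, and the shrinkage step makes that very correction. They also all follow from one slope, which the plan reports. They show what an apparent plot would conceal, not what a corrected curve would add beyond the slope.

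A reader might also infer that the plan will display a slope of 1.18. It does so only if the shrunken model is plotted on the development data, which no section says. The calibration paragraph speaks of the developed model, most naturally the one before shrinkage.

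Two further points stand. An apparent curve is not useless: maximum likelihood fixes the overall slope, but a smoothed curve can still show local or non-linear misfit. And that the apparent plot is the only one is inferred from where the sentence sits and from the silence of the bootstrap text, which refers to cited methods for its detail. If a corrected plot is intended, the plan should say so.

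Finally, a corrected curve will be weak at the top. Assume a normal linear predictor with the plan's R-squared and outcome proportion (SD 1.09, centre −0.60). The share of predictions at 80% or above is then P(Z > (1.386 + 0.60)/1.09) = 0.034, or about 9 of 262. With the spread inflated by 1/0.85 (SD 1.28, centre −0.64) it is 0.057, or about 15.

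**Conclusion.** The point holds as a gap in how calibration is displayed. The plan describes one calibration plot, places it where it says calibration is perfect, leaves the plotted model unstated, and corrects only single numbers for optimism. It does not leave overfitting uncorrected, and the final coefficients are not in question.

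At the plan's own S = 0.85, an apparent plot of the unshrunken model would miss differences of about 3 to 5 percentage points at predictions of 70%, 80% and 10%. A development-data plot of the shrunken model would have a slope of about 1.18 that does not reflect a fault in the model. Both figures assume S = 0.85. The risk-scale figures also assume that shrinkage acts around the overall logit. The realised slope after shrinkage would be 1 over the bootstrap estimate, which averaged 1.21 and 1.25 under the two simulated patterns.

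The weight is modest, but the change is worth making because the aim is individual absolute risk and no external validation is scheduled.

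**What to change.** Add to the internal validation text:

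- In each of the 200 bootstrap samples, after repeating selection and fitting, compute a smoothed calibration curve of the bootstrap model in its own sample and in the original data, on a fixed grid of predicted risk. Average the difference over samples and subtract it from the apparent curve.
- Keep the grid within the observed range of predicted risk, and state the smoother.
- State whether the curve is computed within each imputed dataset or averaged over the 50 imputations. The plan does not say how bootstrap and imputation are combined, and the numerical statistics need the same decision.
- Present the corrected curve with the optimism-adjusted slope as the calibration result. State for each curve whether it is for the model before or after shrinkage, and label any development-data curve as apparent.

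If this is not adopted, the minimum is to label the plot as apparent, name the model, and print the optimism-adjusted slope beside it.

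The cost is SAP wording and modest code on fits already planned, with no new data. The downsides are the extra work of combining bootstrap and imputation, and a curve that is imprecise at the extremes with about 262 participant-seasons, which the report should say.
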